1 **Hypolipidemic and Antioxidant Capacity of Spirulina and Exercise**

2 NCT number: NCT02837666.

3 Date: April 27, 2017

4 Responsible: [name] [name]

5 Autonomous University of Ciudad Juárez, México

6 e-mail: [contact]

7 **Abstract**

8 **Introduction:** In order to reduce cardiovascular diseases risk factors, a healthy  
9 diet must include dietary antioxidants from different sources (e.g. *Spirulina*  
10 *maxima*) and regular practice of exercise should be promoted.

11 There is a little evidence from animal studies that *Spirulina maxima* and exercise,  
12 decreases cardiovascular diseases risks factors. However, very few studies have  
13 proven the independent or synergistic effect of *Spirulina maxima* plus exercise in  
14 humans. Therefore, this study pretends to address this independent and  
15 synergistic effect in overweight and obese subjects participating in a systematic  
16 physical exercise program at moderate intensity on general fitness, plasma lipid  
17 profile and antioxidant capacity in overweight and obese subjects.

18 **Methods and analysis:** Through a randomized, double-blind, placebo-controlled,  
19 and a counterbalanced crossover study design, eighty healthy overweight, and  
20 obese subjects will be evaluated during a twelve-week isoenergetic diet,  
21 accompanied by 4.5 g a day of *Spirulina maxima* intake and/or a physical  
22 systematic exercise program at moderate intensity. Body composition, oxygen  
23 uptake, heart rate, capillary blood lactate, plasma concentrations of triacylglycerols,  
24 total, low and high-density lipoprotein cholesterol, antioxidant status, lipid oxidation,  
25 protein carbonyls, superoxide dismutase, catalase, glutathione, glutathione  
26 peroxidase, glutathione reductase, and paraoxonase will be assessed.

27 **Ethics and dissemination:** This study and all the procedures have been approved  
28 by the Universidad Autonoma de Ciudad Juarez Bioethics Committee. Moreover,

29 findings will be disseminated through peer-reviewed journals, national and  
30 international conferences.

31 **Trial registration number:** ClinicalTrials.gov: NCT02837666.

32 **Keywords:** Spirulina, dyslipidemias, oxidative stress, exercise, body fat,  
33 antioxidant.

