### 83 **Methods/Design**

#### 84 **Hypothesis**

85 *Spirulina maxima* intake and a dosed physical activity program will improve lipids  
86 profile, general fitness and antioxidant status in overweight and obese subjects.

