#### 87 **Objectives**

88 The ISESE project's main objective is to demonstrate that ingestion of *S. maxima*  
89 and a dosed physical activity program will decrease, both independently and  
90 synergistically, some CVD risks in overweight and obese subjects.

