#### 100 **Participants' eligibility**

101 The inclusion criteria will be the age between 18 and 45 years old of both sexes:  
102 40 overweight (Body mass index (BMI): 25-29.9 kg/m^2) and 40 obese (BMI: >30  
103 kg/m^2). The subjects' exclusion criteria will be: drinking more than 100 mL of  
104 alcohol a week, taking drugs and/or food or vitamin supplements, having a chronic  
105 disease, or having a physical or electrocardiographic injury that prevents them from  
106 engaging in any regular physical exercise. The elimination criteria will be that the  
107 program subjects' attendance will be lower than 80% and/or 20% change in their  
108 body weight during study.

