## 162 **Maximum intensity tests**

163 Each subject will participate in four stress tests performed at maximum intensity  
164 (MIT) during the study; during MIT record, consumed O2 and produced CO2 will be  
165 taken by a gas analyzer (Cortex MetaLyzer® 3B, Germany), HR with a Polar H7  
166 sensor (Polar Electro, Lake Success, NY), and lactate in capillary blood samples  
167 will be assayed in a YSI 1500 Sport Lactate Analyzer (YSI Life sciences, OH,  
168 USA). The MIT protocol consists of using a cycle ergometer (Monark ergomedic  
169 828 E; Monark exercise AB, 105 Vansbro, Sweden) initiating with a workload of 50-  
170 75 W with increments of 15-30 W every 3 min for until 15 min or when the subject  
171 could no longer pedal more than 40 revolutions/min, finishing the test when  
172 reaching 90-100 % of the maximum HR reserve; MIT will not be valid for less than  
173 9 min (Figure 2). At the end of each increment load (3 min), capillary blood  
174 samples will be taken to determine lactate, and the physical perceived effort will be  
175 registered by using the Borg scale. Measurements of HR, glucose and blood  
176 pressure will serve to take care of the subject's health during each MIT.

177 Before the first MIT, subjects will decide to be in the GEx or GNEx, and then they  
178 will be divided randomly for the treatment, which consists in a daily dosage of 4.5 g  
179 of Spirulina or placebo in capsules which will be recommended the subjects to  
180 consume them before each meal every day during six weeks. The day after the  
181 first supplementation period, subjects will come back to perform the second MIT

182 with identical conditions to the first one. The third MIT will be performed after a  
183 washout period of two weeks to remove the effects of treatment and avoid any  
184 possible delayed effect of *S. maxima* in the organism. The last MIT will be  
185 performed after the second treatment with identical conditions to the previous three  
186 times. General fitness parameters will be measured the same day of all the MITs to  
187 have accurate results.

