### 199 **Adherence assessments**

200 Multiple methods will be used to assess treatment adherence including pill  
201 counting; reasons for non-compliance, and use of the capsules. Participants will  
202 return each week to receive new capsules. All treatment data will be recorded on  
203 the appropriate case report form.

204 **Dietary analysis**

205 All participants will be subjected to a nutritional survey to define the daily calories  
206 required to establish a custom diet. Dietary intake will be monitored through  
207 retrospective methods including the 24 h recall (which investigates intake over a  
208 specific day), and the food frequency questionnaire (a summary of usual intake of  
209 different categories of foods). These accurate and validated techniques allow  
210 quantifying the types and quantities of foods and beverages consumed during the  
211 period of interest in the past. Dietary intake evaluations will be performed at each  
212 MIT of the study in order to record the possible variability in food consumption  
213 patterns.

214 **Physical exercise protocol**

215 General health assessment and physical activity questionnaires (PAR-Q and YOU)  
216 will be conducted; this will be done to ensure that there are no physical  
217 impediments to exercise. GEx participants are going to exercise five days a week  
218 with the following protocol: between 5 and 10 min of warm-up exercise, between  
219 20-30 min muscular endurance exercise and 20-30 minutes of aerobic exercise  
220 (cardiovascular exercise): walking, jogging, running and/or cycling. Three days a  
221 week aerobic intensities will be between 60% and 80% and two days between 70%  
222 and 90% of the maximum HR reserve, and five final minutes of stretching.

223 **Sample collection and biochemical analysis**

224 Blood samples (8 mL) will be collected before and after each MIT from the  
225 antecubital vein into ethylenediaminetetraacetic acid (EDTA) tubes after 10-12 h of

226 fasting, plasma from blood samples will be obtained by refrigerated centrifugation  
227 (4°C) at 5 000 g for 10 minutes. Plasma glucose TC, HDL-c, LDL-c, and TAG  
228 concentrations will be analyzed by using standard enzymatic procedures (Jas  
229 Diagnostics, Inc. Mexico) with a spectrophotometer (Genesys 10 UV; Thermo  
230 Electron Corporation, USA). Plasma will be used to measure MDA and GSH  

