### 238 **Statistical analysis**

239 To evaluate data distribution, normality and homoscedasticity tests on each of  
240 response variables analyzed will be conducted. In order to analyze differences  
241 between variables before and after the study and between the groups, an ANOVA  
242 test will be performed. To analyze possible associations between variables, a  
243 bivariate correlation analysis will be used. To analyze independence between  
244 variables, a multiple regression analysis will be performed. The software to use is  
245 GraphPad Prism 6.

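### Participants are eliminated on attendance and weight change that arise only after allocation, and no analysis set keeps them; if attendance means exercise sessions, the exercise effect is probably modestly overstated

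*Combined protocol and SAP*

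**What the plan says.** The Participants' eligibility section gives inclusion criteria, exclusion criteria and then a third list: "engaging in any regular physical exercise. The elimination criteria will be that the" "program subjects' attendance will be lower than 80% and/or 20% change in their" body weight during the study. The section does not say which attendance is counted, over what period, or what elimination does to data already collected.

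The Statistical analysis section specifies distribution checks and, for differences "between variables before and after the study and between the groups, an ANOVA" test, followed by correlation and multiple regression. Neither it nor any other section available for review names an analysis set, a missing-data rule, or the handling of eliminated participants. Study design raises the sample from 73 to 80 to allow for desertions and does not mention eliminations.

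Three other places bear on who is affected:

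- **Meaning of program.** The Abstract ("systematic exercise program at moderate intensity. Body composition, oxygen"), the Hypothesis ("intake and a dosed physical activity program will improve lipids") and the Objectives ("and a dosed physical activity program will decrease, both independently and") all use the word for exercise or physical activity.
- **Attendance burden.** Under Physical exercise protocol, "GEx participants are going to exercise five days a week". Under Adherence assessments, every participant in either group comes back weekly for capsules.
- **Choice of group.** Under Maximum intensity tests, "Before the first MIT, subjects will decide to be in the GEx or GNEx, and then they" are randomised to S. maxima or placebo.

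**The concern.** Attendance accrues over the program and weight change is measured during the study, so neither can act as a screening rule. If eliminated participants leave the analysis, the people analysed are chosen partly by how they behaved after allocation.

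The main objective is an independent and a synergistic effect of S. maxima and the activity program. If the attendance rule filters mainly GEx, the exercise contrast sets GEx members who kept attending against a largely unfiltered GNEx. That is a second selection, on adherence, added to the participants' own choice of group. The analysis plan cannot undo the choice of group, but it can avoid the second selection at little cost.

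**Working it through.** **The plan's own figure.** The 73 cannot be reproduced, because no effect size, standard deviation, test or sidedness is given. The step to 80 leaves room for 80 − 73 = 7 losses from all causes, 7/80 = 8.75%. The point does not turn on this figure.

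**Where the attendance line falls.** The documents do not say which weeks count. If they are the 12 treatment weeks at five sessions each, there are 5 × 12 = 60 sessions. Missing 12 leaves 48/60 = 80% (kept). Missing 13 leaves 47/60 = 78.3% (eliminated). So just over one missed session a week crosses the line. If the two washout weeks count as well, there are 70 sessions and the line is crossed at 15 missed (55/70 = 78.6%).

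**How many might be eliminated.** The documents give no rate. As an illustration, assume each attendance is independent with the same probability p. The chance of elimination is P(X < 48) with X ~ Bin(60, p) for exercise sessions, and P(X < 10) with X ~ Bin(12, p) for weekly visits.

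| p | 60 sessions | 12 weekly visits |
|---|---|---|
| 0.80 | 42% | 44% |
| 0.85 | 11% | 26% |
| 0.90 | 0.6% | 11% |

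Elimination rates of 10% to 30% are thus plausible but not certain. If the weekly visits count, GNEx could lose as many as GEx, or more.

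**Exercise contrast, if only GEx is filtered.** Let q be the fraction of GEx eliminated. Let those retained gain a benefit B and those eliminated gain gB. The mean benefit in all who chose GEx is B[(1 − q) + qg]; the retained sample shows B. The overstatement is 1/[(1 − q) + qg] − 1.

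| q | g = 0.75 | g = 0.5 |
|---|---|---|
| 0.10 | 1/0.975 − 1 = 2.6% | 1/0.95 − 1 = 5.3% |
| 0.20 | 1/0.95 − 1 = 5.3% | 1/0.90 − 1 = 11.1% |
| 0.30 | 1/0.925 − 1 = 8.1% | 1/0.85 − 1 = 17.6% |

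Both q and g are assumptions.

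**S. maxima and synergy contrasts.** In the crossover, each person's S. maxima effect is the difference between that person's two treatment periods. A stable characteristic of the person, including general adherence, enters both periods and cancels. Dropping a person removes the whole difference. Synergy is the mean of these differences in GEx minus their mean in GNEx, so the same cancellation applies. Bias arises only if elimination depends on the response in a particular period, or on the size of the person's S. maxima effect. Otherwise the cost is precision and generalisability.

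For synergy, assuming 40 choose each group and n remain in GEx, the standard error grows by the factor √[(1/40 + 1/n)/(2/40)]:

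- n = 36 (10% eliminated): 1.027
- n = 32 (20%): 1.061
- n = 28 (30%): 1.102

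That is 3% to 10%.

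**The case against.** The strongest reply is that the randomised comparison is the one least exposed. Only S. maxima against placebo is randomised; exercise is self-chosen, so that contrast has no randomisation to protect. Keeping everyone would leave the self-selection, of unknown size, in place. This stands: the percentages above are an increment to an estimate that is already non-randomised. They still matter, because this increment is avoidable.

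Second, the skew towards GEx is an inference. The eligibility section does not define attendance, and all participants have weekly capsule visits. This also stands. The use of the word elsewhere and the five-day schedule make the exercise reading the more natural one, but they do not settle it.

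Third, the Hypothesis and Objectives speak of a dosed program. If the target is the effect of the delivered dose, people who attended come closer to it, although they remain a selected group. The documents do not state the target, so overstated here means relative to everyone who chose GEx.

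Fourth, elimination might mean only that a person leaves the program, with the data kept. The text does not exclude this, and a reader should not take it as stated that data are discarded. Dropping them is the ordinary reading, and nothing available for review says otherwise.

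**Conclusion.** The point holds, as a cheap improvement. The plan carries an elimination rule that operates after allocation and defines no analysis set that keeps the people it catches. If program attendance means exercise sessions, the exercise effect is overstated by about 3% to 18%, assuming that 10% to 30% of GEx are eliminated and that they gain half to three quarters of the benefit. If capsule visits also count, GNEx is affected too and the direction cannot be given. How often the 20% weight condition would be met cannot be judged from the documents.

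Three stronger conclusions might be inferred, and the documents support none of them:

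- **The rule biases the randomised S. maxima comparison.** Within-person differencing removes stable differences between people. Nothing in the documents shows that elimination would follow period-specific response or the size of the S. maxima effect.
- **The rule biases synergy.** The same argument applies. Only a precision cost is shown, a 3% to 10% larger standard error under the same assumed rates with 40 per exercise group.
- **The trial becomes underpowered.** With no stated effect size or test, that cannot be established.

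**What to change.** - Define elimination, including what it means for data, and define program attendance: which visits or sessions count, and over which weeks.
- Make the primary analysis all randomised participants with any post-baseline lipid value, by assigned sequence and by the exercise group chosen at entry, using all available period data. A mixed model that accommodates incomplete periods is one suitable method.
- Retain lipid data already collected, and the already scheduled fasting samples, for participants who cross the thresholds.
- Use the 80% and 20% thresholds only for a labelled per-protocol sensitivity set.
- Report eliminations with reasons by sequence, period and exercise group.

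Whether participants who cross a threshold continue the intervention or the stress tests is left to the sponsor.

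The cost is a little more analysis work, follow-up of the scheduled samples, and a possibly smaller exercise estimate. No participants are added.

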#### 109 **Call to participation, ethics and safety procedures**

110 University students of Ciudad Juarez, Mexico with overweight and obesity will be  
111 personally invited to participate. Participants will be informed of the purpose of the  
112 study, and of the physical, clinical and biochemical procedures, benefits, physical  
113 intensity tests, and risks, all before beginning the clinical trial. To guarantee the

114 good physical and mental health of the participants at the beginning of all the  
115 studies, a medical clinical laboratory study examination and an electrocardiography  
116 at rest tests will be performed. Noting that investigators are trained in  
117 cardiopulmonary reanimation and that the laboratory has the necessary  
118 communication tools and channels to perform emergency procedures. This study  
119 and all the procedures have been registered appropriately in ClinicalTrials.gov  
120 database (NCT02837666) and approved by the Bioethics Committee of the  
121 Universidad Autonoma de Ciudad Juarez (Supplementary files). That participants'  
122 acceptance formalized by means of written informed consent and their anonymity  
123 and confidentiality will be strictly enforced. This study will be conducted in  
124 compliance with the principles of the Declaration of Helsinki.

### 125 **Baseline measurements**

126 A day before beginning the treatment, subjects will visit the laboratory for baseline  
127 measurements. Body mass will be measured with subjects lightly dressed and  
128 barefoot in an electronic balance, and standing height with a stadiometer. Body fat  
129 percentage will be measured by plethysmography method (BodPod, USA), electric  
130 bioimpedance (in body 160, US), and by dual-energy X-ray absorptiometry (DXA)  
131 (Prodigy v6.8; GE Lunar, Milwaukee, WI) according to manual guidelines.  
132 Anthropometric parameters will be taken by the standardized method of the  
133 International Society for the Advancement of Kinanthropometry (ISAK), and  
134 according with ISAK Anthropometry Accreditation protocols . Researchers are  
135 standardized in handling equipment and procedures.

### 136 **Study design**

137 The study consists of *S. maxima* treatment during 14 weeks in a randomized,  
138 double-blind, placebo-controlled, and counterbalanced crossover design, aimed to  
139 eliminate inter-individual bias as well as boosting the reliability of final results;  
140 moreover, this design is commonly used in clinical trials in order to have better  
141 results and conclusions . Eligible participants (n= 80) will be divided into two  
142 groups, one with systematic practice of physical exercise (GEx) and other one  
143 without it (GNEx). The participants of each group will be randomized in equal  
144 proportions between *S. maxima* and placebo treatment, receiving either 4.5 g daily,  
145 in a non-transparent capsule during 12 weeks (6 weeks for the first treatment - 2  
146 weeks of washout period - 6 weeks for the second treatment) (Figure 1). Before  
147 any reported allergic reaction occurs, the treatment will be discontinued.

148 To maintain the overall quality and legitimacy of the clinical trial, code interruptions  
149 should occur only in exceptional circumstances when knowledge of the actual  
150 treatment is essential for further management of the participant. Investigators are  
151 encouraged to discuss with a Medical Advisor if they believe that unblinding is  
152 necessary. Unblinding should not necessarily be a reason for study  
153 discontinuation.

154 A student outside the research team will feed data into the computer in separate  
155 datasheets, so that the researchers can analyze the data without having access to  
156 information about the allocation treatments, storing all the participants' files in  
157 numerical order in a safe and accessible place. The participants' files will be stored  
158 for a period of five years after the end of the study.

159 The sample size was determined by using the statistical program G\*Power ,  
160 selecting a sample of 73 subjects with  $\alpha = 0.05$  and  $p = 0.85$ . This sample will be  
161 fixed to 80 subjects in order to anticipate the possible desertions from the study.

## 162 **Maximum intensity tests**

163 Each subject will participate in four stress tests performed at maximum intensity  
164 (MIT) during the study; during MIT record, consumed O2 and produced CO2 will be  
165 taken by a gas analyzer (Cortex MetaLyzer® 3B, Germany), HR with a Polar H7  
166 sensor (Polar Electro, Lake Success, NY), and lactate in capillary blood samples  
167 will be assayed in a YSI 1500 Sport Lactate Analyzer (YSI Life sciences, OH,  
168 USA). The MIT protocol consists of using a cycle ergometer (Monark ergomedic  
169 828 E; Monark exercise AB, 105 Vansbro, Sweden) initiating with a workload of 50-  
170 75 W with increments of 15-30 W every 3 min for until 15 min or when the subject  
171 could no longer pedal more than 40 revolutions/min, finishing the test when  
172 reaching 90-100 % of the maximum HR reserve; MIT will not be valid for less than  
173 9 min (Figure 2). At the end of each increment load (3 min), capillary blood  
174 samples will be taken to determine lactate, and the physical perceived effort will be  
175 registered by using the Borg scale. Measurements of HR, glucose and blood  
176 pressure will serve to take care of the subject's health during each MIT.

177 Before the first MIT, subjects will decide to be in the GEx or GNEx, and then they  
178 will be divided randomly for the treatment, which consists in a daily dosage of 4.5 g  
179 of Spirulina or placebo in capsules which will be recommended the subjects to  
180 consume them before each meal every day during six weeks. The day after the  
181 first supplementation period, subjects will come back to perform the second MIT

182 with identical conditions to the first one. The third MIT will be performed after a  
183 washout period of two weeks to remove the effects of treatment and avoid any  
184 possible delayed effect of *S. maxima* in the organism. The last MIT will be  
185 performed after the second treatment with identical conditions to the previous three  
186 times. General fitness parameters will be measured the same day of all the MITs to  
187 have accurate results.

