#### 91 **Outcome measures**

92 The primary outcome measure will be changes in the plasma lipid profile after a  
93 six-week of treatment (plasma TAG, TC, HDL-c, and LDL-c by using standardized  
94 enzymatic methods).

95 The secondary outcome measure will be changes in general fitness (maximal  
96 oxygen uptake ( $VO_2$  max), heart rate (HR), in onset blood lactate accumulation,  
97 and body fat mass); as well as changes in redox status (malondialdehyde (MDA),  
98 protein carbonyls, paraoxonase (PON1), superoxide dismutase (SOD), catalase  
99 glutathione (GSH), glutathione reductase (GR), and glutathione peroxidase (GPx).

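### The test end points do not secure the VO2max outcome: a valid test may be submaximal, and the 15-min limit can hide a gain

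*Combined protocol and SAP*

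**What the plan says.** **Outcome measures.** "The secondary outcome measure will be changes in general fitness (maximal" oxygen uptake, written as VO2max, then "heart rate (HR), in onset blood lactate accumulation", and body fat mass. The section does not say whether heart rate means resting, same-load or end-test heart rate.

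**Maximum intensity tests.** "Each subject will participate in four stress tests performed at maximum intensity". The loading scheme and end points run in one sentence: "initiating with a workload of 50" to "75 W with increments of 15-30 W every 3 min for until 15 min or when the subject" "could no longer pedal more than 40 revolutions/min, finishing the test when" "reaching 90-100 % of the maximum HR reserve; MIT will not be valid for less than" 9 min. Read together, three events can end a test: 15 min elapsed, cadence no longer above 40 rev/min, or a heart rate somewhere in the 90-100% band. Gas exchange and heart rate are recorded during the test, and lactate and perceived effort at the end of each 3-min stage. Later tests are to be run under the same conditions as the first, but the section does not say that this covers starting load and increment.

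**Not stated:** a criterion for accepting a VO2 value as maximal, the source of the maximum heart rate, which end point takes precedence, and any record of why a test stopped.

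**The concern.** VO2max is meaningful as an outcome only if the test is shown to reach a maximum. Here two of the three end points are preset: a clock time and a heart-rate band. Following the plan exactly, a site could label a load-limited or submaximal uptake as VO2max.

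The trial's objective is the separate and joint effect of Spirulina and exercise. Fitness gains are most to be expected in the exercising group, so a limit that cuts off gains would act mostly there and pull that contrast towards no difference. Different stop reasons at different visits would also make a participant's four end-test values hard to compare, which matters in a crossover built on within-person change.

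**Working it through.** The plan gives no figure of its own on this point, so there is none to reproduce. The check applies arithmetic to the test's own limits.

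**Inputs from the protocol.** Start 50-75 W; increment 15-30 W every 3 min; limit 15 min; minimum valid duration 9 min; heart-rate end point 90-100% of reserve; age 18-45 years.

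**Inputs assumed**, because the documents give none. True VO2max 20-40 mL/kg/min, with resting uptake 3.5; percent heart-rate reserve equal to percent VO2 reserve; maximum heart rate 220 minus age, so 175-202 bpm; resting heart rate 60-80 bpm.

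**1. Time limit.** Stages = 15/3 = 5. Last load = start + 4 × increment:
- 50 + 4×15 = 110 W
- 75 + 4×15 = 135 W
- 50 + 4×30 = 170 W
- 75 + 4×30 = 195 W

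With the same start and increment, two tests that both run to 15 min end at the same work rate. Uptake at a given work rate is set mainly by the load, so a gain between those tests is largely hidden. As an illustration only, an assumed cycling cost of 10.8 × W/kg + 7 puts the ceiling at 10.8×110/85 + 7 = 21.0 to 10.8×195/85 + 7 = 31.8 mL/kg/min at 85 kg, and at 17.3 to 37.1 over 70-115 kg.

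**2. Understatement at the heart-rate stop.** VO2 at 90% = 3.5 + 0.9 × (VO2max − 3.5).

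| True VO2max | Recorded at 90% | Shortfall |
|---|---|---|
| 20 | 18.35 | 8.25% |
| 30 | 27.35 | 8.8% |
| 40 | 36.35 | 9.1% |

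**3. Does a change still show?** Take a true rise from 30 to 33, a gain of 3.0.
- Both tests stopped at 90%: 27.35 to 3.5 + 0.9×29.5 = 30.05, a recorded gain of 2.70, or 90% of the true gain.
- First test at 100%, second at 90%: 30.05 − 30.00 = 0.05.
- First test at 90%, second at 100%: 33.00 − 27.35 = 5.65.

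The last two are the extremes. If the stop were uniform over the band, then at VO2max 30 the spread is 0.1×26.5 = 2.65, the SD per test is 2.65/√12 = 0.77, and the SD of a two-test difference is 0.77×√2 = 1.1 mL/kg/min.

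**4. End-test heart rate.** Band width = 0.1 × (maximum − resting): 0.1×(175 − 80) = 9.5 bpm to 0.1×(202 − 60) = 14.2 bpm. For tests ended by this rule, end-test heart rate can vary only within that width.

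**5. What every valid test contains.** Nine minutes is three completed stages. The third-stage load is start + 2 × increment: 50 + 2×15 = 80 W to 75 + 2×30 = 135 W. If loads are fixed per participant, the first three stages are common to all of that participant's valid tests.

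**The case against.** **VO2 is not fixed by the rule.** A reader might infer that stopping on heart-rate reserve leaves VO2 unable to show a training effect. The documents do not support that. The rule constrains heart rate, not oxygen uptake, and at a constant 90% stop 90% of a true gain is recorded. Drift within the band is mainly lost precision, not bias towards no effect. This objection stands.

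**Peak heart rate is not a named outcome.** The protocol says only heart rate. Resting or same-load heart rate could change freely. This stands, so the point about end-test heart rate is conditional.

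**General fitness is wider than VO2max.** Fat mass does not depend on the test, and lactate is sampled at every stage. This also stands.

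**The ceiling may rarely be reached.** It affects only those who get to 15 min before the other two end points, and the load ranges may allow tailoring. The number affected is unknown, so no size can be given for the bias in the exercise contrast. Nor do the documents show that it would concentrate in the second period.

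**Exhaustion is possible.** Loss of cadence may end a test at exhaustion, and 100% lies within the band, so some tests may be maximal. But without a criterion or a recorded stop reason, the analyst cannot tell which.

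**The wording is ambiguous.** The heart-rate clause could describe the effort expected at the end instead of a separate stop. Figure 2, which is captioned as the test design, was not available for this review. Even on that reading, the 15-min limit and the missing maximality criterion remain.

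**Conclusion.** The concern holds in a limited form. The end points do not secure a VO2max: a test that counts as valid may be submaximal, and nothing in the plan separates such tests from maximal ones. The time limit is the part that can hide change, and only for participants who reach 15 min at two tests with the same loads; their last load is then the same value, between 110 and 195 W. The heart-rate band understates VO2 by up to about 9% and adds test-to-test noise, with an SD of roughly 1.1 mL/kg/min for a difference under a uniform stop at VO2max 30. It does not by itself prevent VO2 from showing change. End-test heart rate, if meant, is largely set by the rule.

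The load figures follow from the protocol alone. The percentage and noise figures rest on equating percent heart-rate reserve with percent VO2 reserve, and the bpm figures on the assumed heart rates. The point concerns secondary outcomes only; the primary lipid outcome and fat mass are untouched.

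**What to change.** Leave the termination rule as it is and change what is derived from the test:

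- Report the end-test uptake as VO2peak, and record the stop reason for every test.
- State that the requirement for the same conditions covers starting load and increment, so that each participant has the same values at all four tests.
- Define the heart-rate outcome as heart rate at a fixed submaximal stage common to that participant's four tests, chosen in advance. The first three stages are completed in every valid test.
- Analyse lactate at that same stage.
- Analyse load and VO2 at a prespecified lactate concentration by interpolation between stages, and say how a test that does not reach that concentration is handled.
- Do not use VO2max extrapolated from the heart-rate line, or VO2 at a fixed percent of heart-rate reserve, unless the source of the maximum heart rate is stated.

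The cost is protocol and analysis wording, plus one field for the stop reason. Gas exchange, heart rate and stage-by-stage lactate are already collected. The small downside is that fitness is reported as VO2peak and submaximal measures, not as VO2max.
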